9.6 Exploratory objectives (to be reported and funded separately)

There are no additional exploratory/mechanistic objectives/outcomes in this study. However, all OP Non-STOP participants will be asked to give their consent for their personal details to be shared with the Non-Arthroplasty Hip Registry (NAHR); which is the national UK registry of hip surgery that does not involve joint replacements. Registration on the NAHR will enable long term follow up of study participants at a later time point. This follow-up falls outside the scope of this trial and additional approvals and funding would be required for any future research.

10 STUDY DESIGN AND SETTING

The OP Non-STOP study is a multi-centre, two arm, parallel design, superiority, randomised controlled clinical trial.

The study will recruit 216 children (108 in each of two arms) with Perthes' disease from a minimum of 28 sites in the UK. Participants will be randomised to receive either containment surgery or active containment.

A study flow chart is provided in APPENDIX 1 – STUDY FLOW CHART.

10.1 Recruiting sites/site types

Participants will be recruited from a minimum of 28 orthopaedic departments who have surgeons specialising in the treatment of childhood disease.

Treatment of all severities of Perthes' disease tends to be focused in specialist units in the UK. Sites that have been identified as potential recruiting sites for this study have seen between 3 and 20 eligible cases per year.

Refer to section 27 for information on identification and management of sites.

10.2 Collection of outcome data and follow-up assessments

Data will be primarily collected electronically. The study will be made efficient by ensuring that all outcomes are collected via a SMS text message with a link to an electronic Case Report Form (eCRF) amongst those with a smart phone or an e-mail link to an eCRF for those with internet access but no smart phone. If needed, questionnaires can be completed in clinic with the research team at site or over the phone with the central team.

Study materials will be optimised using age-appropriate multimedia resources, developed with knowledge acquired through members of the OP Non-STOP teams work as part of the NIHR TRECA study [26].

10.3 Countries of recruitment

UK.

10.4 Duration of participant involvement

Participants will be in the study for approximately 36 months from randomisation to last protocol visit.

10.5 Post-study treatment/care and follow-up

Following a participant's allocated containment surgery or active containment, they will receive standard NHS care. All patients will receive analgesia as per local/best practice guidelines and physiotherapy where required.

10.6 Central review procedures

The degree of residual deformity will be quantified (Waldenström grade and Stulberg classification) on the central review CRF.

10.7 Use of Registry/NHS England data

Parents and children will have the option to consent to their contact details and the child's personal details being shared with the NAHR; which is the national UK registry of hip surgery that does not involve joint replacements. Registration on the NAHR will enable long term follow-up of study participants at a later time point. This follow-up falls outside the scope of this study and additional approvals and funding would be required for any future research.

10.8 Expected recruitment rate

The pilot phase will involve recruitment in 15 centres over a 12 month period. The main recruitment phase will then continue for an additional 18 months and at least 28 centres.

Recruitment projections, informed by data from the BOSS study, are based on a recruitment rate of 0.35 participants per site per month.

10.9 Equality, diversity and inclusion for study participants

There is a very strong socioeconomic gradient in Perthes' disease, with deprived White communities predominantly affected. We are aware, through the prior BOSS study, of the centres that have a particularly high burden of disease; we will therefore prioritise centres serving deprived communities (particularly in the North West and North East of England) and optimise the research processes to best engage this participant group [27].

The team have carefully considered digital inclusivity, particularly given the socioeconomic gradient associated with Perthes' disease. Both children and families in the study advisory groups had a strong preference for electronic media and data collection, rather than paper, and did not feel that the use of email/ smartphones would be a barrier to recruitment or follow-up. This is backed up by a recent publication on digital inclusion for UK children [28]. However, paper copies of study documents will be made available when requested. The PROMIS Mobility primary outcome tool must be collected electronically (as this is a computer adaptive test), so to facilitate this, families can choose to be followed up by telephone if more convenient.

During the early phase of the COVID-19 pandemic, 8% of children (aged 3-17 years) did not have home access to a desktop computer, laptop or netbook which is connected to the internet. However, when access to smartphones in a household was accounted for, this rate was lower than 1% of households [29]. Our other HTA trials (FORCE, SCIENCE, CRAFFT) have recruited patients in similar paediatric orthopaedic populations using email and smartphone technology throughout; with all digital materials optimised for use on smartphones. During the internal pilot, we will monitor for any issues by analysing screening logs and exclusion reasons.

10.10 End of study

The end of study is the point at which all CRF and non-CRF data relating to the study primary and secondary outcomes has been entered/received (or collected if non-CRF data) and all queries resolved. The study will stop randomising participants when the stated number of patients to be recruited is reached.

The Sponsor and the CI reserve the right to terminate the study earlier at any time. In terminating the study, they must ensure that adequate consideration is given to the protection of the participants' best interests.

11 PARTICIPANT ELIGIBILITY CRITERIA

Participant eligibility will be confirmed by a suitably qualified and experienced individual who has been delegated to do so by the Principal Investigator (PI).

11.1 Timing of eligibility assessment

Eligibility will be assessed upon initial entry into the study and confirmed at the point of randomisation.

11.2 Overall description of study participants

The OP Non-STOP study will recruit children aged 5-12 years old with Perthes' disease.

Written informed consent/assent must be obtained before any study specific procedures are performed.

11.3 Inclusion Criteria

A patient will be eligible for inclusion in this study if **ALL** of the following criteria apply:

- Radiographic evidence of Perthes' disease,
- Radiographs demonstrate that the disease is in the initial, sclerotic or fragmentation stage,
- Aged 5 to 12 years inclusive,
- Willing and able to give informed assent/consent.

Note: Patients may be enrolled with bilateral Perthes' Disease - though patients can only ever be enrolled once into the study. If one side has old disease (i.e. hip in reossification or healed stage of disease) and is not already included in the study, then the newly affected hip can be enrolled (i.e. that hip in the initial, sclerotic or fragmentation stage). If both hips have new disease, then the hip considered the most severely affected will be considered the hip of interest and the surgeon must specify which hip is the unit of randomisation.

11.4 Exclusion Criteria

A patient will not be eligible for the study if **ANY** of the following apply:

- There is evidence that the patient and/or parent would be unable to adhere to the study procedures or complete follow-up, such as insufficient comprehension,
- Child has undergone prior containment surgery on the affected hip (i.e. the hip to be randomised),
- The child has previously been enrolled into the OP Non-STOP Study.

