8.2 Current practice – The British Orthopaedic Surgery Surveillance (BOSS) Study

Given the controversy, there is substantial variation in the treatment of Perthes' disease. This varies from observation without any intervention, to physiotherapy involving activity restrictions and physiotherapy, to surgery involving femoral and/or pelvic osteotomies [3, 8, 9]. Over the last 6 years, researchers in the UK, including the CI of this study, have carefully explored current practice through a nationwide collaboration with the support of parent co-investigators.

In 2016, the National Institute for Health and Care Research (NIHR) funded British Orthopaedic Surgery Surveillance (BOSS) Study, was the first UK study to investigate Perthes' disease [3]. This was a cohort study of incident cases of Perthes' disease. The study collected surgeon reported outcomes on all new cases of Perthes' disease from most children's orthopaedic surgeons in the UK over an 18-month period.

371 children (396 hips) with Perthes' disease were recruited during this time. Two thirds of cases were considered eligible for surgery, and half of these received operative 'containment surgery'. The decision for surgery was almost exclusively driven by the belief and recommendation of the surgeon; with some centres offering and undertaking surgery on the majority of children, whilst other centres did not offer surgery to any. Physiotherapy and advice regarding activity restrictions was the primary treatment in the majority (97%) of those treated without surgery.

The BOSS cohort identified 'clinical irritability' of the hip and 'age' to be the only consistent factors that influenced treatment choices amongst surgeons. Surgery was rarely performed on those under five years old and occurred in more than half of those aged over eight years old. Surgeons operated more frequently on hips that they assessed to be 'irritable' or 'stiff'. The study confirmed the findings of prior literature by demonstrating a worse radiographic prognosis associated with increasing age, female sex, and greater radiographic collapse. However, the 'stiffness' of the hip did not appear to influence outcome. Furthermore, the study found no evidence to suggest that containment surgery improved outcomes. The results of the BOSS study prompted the commissioning brief by the NIHR Health and Technology Assessment (HTA) that has funded this study (NIHR commissioned funding call – 21/586 Management of Perthes' disease in children).

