23.2 Sample Size/Power calculations

172 participants providing data on the PROMIS Mobility Score for children at three years post randomisation (86 in each group) will provide 90% power to detect a difference in means of 5, assuming the standard deviation (SD) is 10 using a two group t-test with a 5% (2-sided) significance level. This is inflated to 216 participants (108 per arm) to allow for 20% attrition.

Raw scores of the PROMIS are translated into standardised T-scores with a population mean of 50 and an SD of 10.

The minimum clinically important difference (MCID) of PROMIS paediatric measures is generally 3.0-5.0 [29,30].

We discussed with children and families the size of the difference they would require to justify surgery, over optimised non-surgical containment. Given that surgery is a considerable intervention in the lives of the child and their family (i.e., the anaesthetic, the pain and scar, admission to hospital, the frequency of the requirement for a second procedure to removal metalwork, along with the lengthy

duration of immobilisation and recovery), families believed that the effect sought should be at the upper range of the MCID. Other studies have similarly highlighted that patients often seek greater effect sizes to warrant bigger surgical interventions than the established MCID [31].

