23.3.1 Primary outcome

The PROMIS Mobility Score for Children at 3 years post-randomisation is the primary outcome of the trial. The primary analysis will use a linear regression model that adjusts for the baseline score and treatment group. As recommended by ICH E9 [39], the model will also adjust for the minimisation factors as fixed effects. An unadjusted analysis, that does not include the baseline score and minimisation factors, will also be performed.

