APPENDIX 2 – DATA COLLECTION

Baseline:

Sourced/Collected by Local Research Team in a clinic visit

- Date of baseline visit
- Participant demographics
 - Ethnicity
 - Biological sex
 - Index of Multiple Deprivation
- Perthes' disease at diagnosis
 - Affected hips (unilateral, bilateral)
 - Current disease stage by radiological status
 - Waldenström classification (0,1A,1B,2A,2B,3A,3B,4)
 - Documented stiffness (stiff, minimal/no stiffness)
 - Degree of deformity (collapse) (>50%, exactly 50%, <50% lateral pillar height)

Direct Participant Report (collected electronically)

- Patient assessment of function
 - o PROMIS Mobility CAT
- Pain
 - Wong-Baker FACES Pain Scale
- Quality of life
 - o CHU-9D
- Impact of the condition
 - o PROMIS Pediatric Family Relationships Questionnaire

Intervention

Surgery

Sourced/Collected by Local Research Team in post-operative period.

- Date of surgery
- Grade of surgeon performing the operation
- Operation type (Varus osteotomy, shelf osteotomy, Salter osteotomy, other redirectional acetabular osteotomy, soft tissue surgery)
- Core decompression performed? (Yes/No)
- Hip distraction performed? (Yes/No)
- Intra-operative complications
- Post-Operative Instructions (Spica/ cast Yes (Duration?)/ No)

Best practice therapy session

Sourced/Collected by Local Research Team in a clinic visit

- Date of session
- Name of physiotherapist delivering session
- Length of session (minutes)
- Content of session included:
 - Individually tailored advice? (Yes/No)
 - Review of walking aids? (Yes/No)
 - Walking aids given (yes/no, if yes what?)

- Reassurance? (Yes/No)
- Education about the condition? (Yes/No)
- Activity modification? (Yes/No)
- Exercise advice? (Yes/No)
- o Pain management information? (Yes/No)
- Goal setting (yes/no)
- What to do if they experience problems? (Yes/No)
 - Any option above if select 'no', will prompt 'Why?'

3 months post randomisation

Sourced/Collected by Local Research Team in a clinic visit / telephone call

Date

Direct Participant Report (collected electronically)

- Patient assessment of function
 - o PROMIS Mobility CAT
- Pain
 - o Wong-Baker FACES Pain Scale
- Quality of life
 - o CHU-9D
- Impact of the condition
 - o Resource use
 - Participation in Education
 - o PROMIS Pediatric Family Relationships Questionnaire

6 months post randomisation

Sourced/Collected by Local Research Team in a clinic visit / telephone call

Date

Direct Participant Report (collected electronically)

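### One hip is randomised but the primary outcome is measured on the child: laterality is missing from the primary model, and the listed data cannot separate surgery on the other hip from surgery on the randomised hip

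*Protocol*

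**What the plan says.** - **Eligibility (Protocol 11.3, 11.4).** Bilateral disease is allowed and each child enters once. Where one hip has old disease, the newly affected hip is enrolled. Where both are new, "If both hips have new disease, then the hip considered the most severely affected will be considered the hip of interest", and the surgeon has to name the hip that is randomised. Prior surgery excludes a child only under this wording: "Child has undergone prior containment surgery on the affected hip (i.e. the hip to be randomised".
- **Outcome (9.2, 9.3).** The primary outcome is the parent-reported PROMIS Mobility score at 36 months, one score per child.
- **Minimisation (15.3).** The factors are age, sex and lateral pillar collapse.
- **Primary model (23.3.1).** "The primary analysis will use a linear regression model that adjusts for the baseline score and treatment group", with the minimisation factors added as fixed effects. Laterality is not included.
- **Data (Appendix 2, which sections 17.3.1 to 17.3.3 cite as the full list).** The baseline form has "Affected hips (unilateral, bilateral" as a single item. The surgery form records the type of operation. Neither lists the randomised hip, the operated side, or earlier or later containment surgery on the other hip.
- **Cross-overs (13.4).** These are described by family and participant and monitored by site. The text does not say how surgery on the other hip is treated.

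**The concern.** In a child with one affected hip, the randomised hip and the child's mobility score refer to the same problem. In a child with two affected hips they do not: the score reflects both hips, while the allocation concerns one.

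Two consequences follow, and they differ in kind.

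1. **State of the other hip at entry.** Old disease, or earlier surgery that section 11.4 permits on that side, affects the score. Allocation is per child, so this is balanced in expectation. It adds variance, of which the baseline PROMIS score removes part.
2. **Treatment of the other hip after entry.** Randomisation does not balance this, because later decisions may depend on the allocation. If a comparator child has containment surgery on the other hip, sites could count it as a cross-over or not. Without a side field, the counts could not be reconciled from the listed data. A later analysis plan can add a covariate, but it cannot recover fields that were never collected.

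**Working it through.** **1. The protocol's own sample size.** Section 23.2 states that the evaluable sample "will provide 90% power to detect a difference in means of 5". Its other inputs are an SD of 10 and a two-sample t-test at the two-sided 5% level. Exact power comes from the noncentral t distribution with 2n − 2 degrees of freedom and noncentrality d / (SD × √(2/n)). With n = 86 per arm: 5 / (10 × √(2/86)) = 5 / 1.525 = 3.28, which gives power of 90.3%. The smallest n reaching 90% is 86 per arm, 172 in all. For 20% attrition, 86 / 0.8 = 107.5, rounded up to 108 per arm, 216 in all. Both stated figures reproduce.

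**2. Share of bilateral children.** Section 8.2 reports "371 children (396 hips) with Perthes' disease were recruited during this time". So 396 − 371 = 25, and 25 / 371 = 6.7%. Applied to the trial: 0.0674 × 216 = 14.6 children, about 7.3 per arm. This is a proxy. It assumes that each extra hip is one bilateral child, and section 8.2 states no 5 to 12 age limit for that cohort.

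**3. Dilution.** Let q be the bilateral share and f the fraction of the effect that a bilateral child's score still shows. The average contrast is 5 × (1 − q(1 − f)). Power is at 86 per arm with SD 10.

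| q | f | Contrast | Power |
|---|---|---|---|
| 6.7% (BOSS proxy) | 0.5 | 4.83 | 88.3% |
| 6.7% (BOSS proxy) | 0 | 4.66 | 86.0% |
| 10% (assumed) | 0.5 | 4.75 | 87.2% |
| 10% (assumed) | 0 | 4.50 | 83.5% |
| 20% (assumed) | 0.5 | 4.50 | 83.5% |
| 20% (assumed) | 0 | 4.00 | 74.2% |

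At the BOSS share the largest loss is 5 − 4.66 = 0.34 points. The values of f, and the 10% and 20% shares, have no source in the protocol.

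**4. Other-hip surgery in the comparator arm.** If every one of the 7.3 bilateral comparator children had it and gained the full 5 points, the loss would be 7.3 / 108 × 5 = 0.34 points. Section 8.2 says that two thirds of cases were considered eligible for surgery and half of those had it, so about one third overall. At that rate, 7.3 / 3 = 2.4 children, 2.4 / 108 = 2.2% of the arm, and 0.022 × 5 = 0.11 points.

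**5. Noise from laterality at entry.** Assume bilateral children score 10 points lower on average. The SD becomes √(100 + 0.067 × 0.933 × 100) = 10.31, and power is 88.5%. Combined with f = 0 it is 83.9%. The chance difference in bilateral share between arms has an SD of √(0.067 × 0.933 × 2/86) = 3.8 percentage points, which moves the contrast by about 0.4 points (one SD). These figures ignore adjustment for baseline PROMIS, so they overstate the noise that remains in the planned model.

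**The case against.** The case against is substantial, and most of it stands.

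- **Contamination.** A reader might infer that the other hip contaminates the comparison unseen. The documents do not support that. Laterality is a baseline item. Section 11.3 requires the randomised hip to be named. Secondary-care use is collected, sites report complications at 18 and 36 months, and routine radiographs are harvested. The forms themselves are not shown, so a side field may exist. What stands is that Appendix 2 does not list one.
- **Cross-over wording.** A reader might also infer that surgery on a comparator child's other hip is by definition no cross-over. Section 13.4 speaks of families and participants, not hips, so the matter is undefined rather than excluded.
- **Earlier surgery on the other hip.** This precedes randomisation and causes no systematic difference between arms. Widening the exclusion in section 11.4 would narrow eligibility in a rare disease without removing any bias.
- **Size and direction.** The comparator-arm scenario of most interest, containment surgery on a second newly affected hip, applies to at most the 6.7%. No rate of other-hip surgery is given, and section 8.2 reports no evidence that surgery improved outcomes. A single direction of bias is not established.
- **Intention to treat (23.4).** Later surgery is part of the pragmatic comparison, and a baseline covariate cannot correct for it. That is right: the covariate addresses only noise.
- **The analysis plan is not shown.** It may already hold a laterality sensitivity analysis. However, section 23.3.1 fixes the primary covariates, and data fields are a protocol matter.

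**Conclusion.** The point holds in a limited form. The unit of randomisation is a hip and the primary outcome belongs to the child. An already collected baseline item that bears on this is left out of both minimisation and the primary model. The listed data also do not allow other-hip surgery after randomisation to be told from surgery on the randomised hip. Only that later surgery could differ systematically by arm.

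The effect is small. At the BOSS-derived share of 6.7%, the loss is at most about 0.3 of 5 points, and nearer 0.1 for comparator other-hip surgery at the BOSS surgery rate. Power falls from 90.3% to 86.0% if bilateral children show no contrast. This rests on the BOSS proxy and on assumed retained effects; a higher bilateral share would make it larger. It does not threaten the validity of the trial. It is worth acting on because the changes are cheap and the missing fields are hard to reconstruct after three years.

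**What to change.** 1. **Section 23.3.1.** Add unilateral/bilateral status as a fixed effect in the primary model, and pre-specify a sensitivity analysis restricted to children with unilateral disease. Cost: one degree of freedom and no new data. The gain in precision is probably small.
2. **Appendix 2 and the forms.** Add the randomised hip, the side of each operation, and containment surgery on the other hip before and after randomisation. Cost: a few fields.
3. **Section 13.4.** State that containment surgery on either hip of a comparator child is counted in the monitored cross-overs, and report it by side (randomised or other hip). Cost: one sentence.

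The exclusion in section 11.4 can stay as it is, and nothing here alters care.

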11.5 Rationale for inclusion and exclusion criteria

The stage of disease ensures that the hip remains 'plastic' (i.e. is in a stage of disease whereby it would be amenable to treatment with containment).

The age of disease reflects the group for which there is clinical equipoise.

11.6 Pre-study screening tests or investigations

There are no pre-study screening tests for inclusion in the study.

